#### 8.3.8. End-of-study / Discontinuation record

The end date of the observation period (date of medical examination on or after Day 28 after the completion of administration) should be recorded. If the patient cannot be followed up until Day 28 after the completion of administration (including Day 28), record date of discontinuation and select only one of the following items that corresponds to the primary reason. If the primary reason corresponds to patient death, necessary information should be recorded in the adverse event field.

- 1. End date of the observation period (date of examination on or after Day 28 after the completion of administration or date of discontinuation)
- Status at the end
  - Completed
  - Symptoms improved
  - Death

- Transferred to other hospital
- Lost to follow-up
- Other

However, if the patient does not return for follow-up visit after the start of administration (including confirmation by telephone, etc.), the information should be recorded in the "lost to follow-up."

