- Resolution of symptoms after worsening of severity during the observation period as of the end date of the observation period: For patients with worsening of severity during the observation period, the absence of symptoms on the end date of the observation period will be considered as resolution of symptoms and evaluated. It consists of the following categories. Even if the end date of the observation period and the date of the highest severity are the same, the patient will be included in the analysis.
 - Resolved, not resolved, unknown (resolution unknown, symptoms not recorded)
- Improvement in severity after worsening of severity during the observation period as of the end date of the observation period: For patients with worsening of severity during the observation period, improvement from the highest severity on the end date of the observation period will be evaluated. It consists of the following categories. Even if the end date of the observation period and the date of the highest severity are the same, the patient will be included in the analysis.
 - Improved, not improved, unknown (improvement unknown, severity not recorded)
- Death from any cause: Death reported by Day 28 after the end of treatment will be considered as an event and evaluated. Death should be confirmed with the outcome information of adverse events. Unknown if no adverse event is reported (Section 10.1 Table 1).
 The number of days from the start date of treatment to the onset date of event will be calculated. If an event including the case of unknown has not occurred, the patient will be censored at the date of the last observation or Day 28 after the end of treatment, whichever is earlier.

The following efficacy endpoint is defined in Efficacy Analysis Sets 2 and 3.

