• Hospitalization for the treatment of infection due to SARS-CoV-2 or death from any cause: Hospitalization for treatment of infection caused by SARS-CoV-2 or death reported by Day 28 after the end of treatment will be considered as an event and evaluated. Death should be confirmed with the outcome information of adverse events. Unknown if neither the status of hospitalization nor the presence or absence of adverse events is reported. When only the status of hospitalization or the presence or absence of adverse events is reported and hospitalization or death applicable to an event is observed, it will be considered as an event, and other cases will be regarded as unknown (Section 10.1 Table 1). In addition, each event of hospitalization and death will be evaluated.

The number of days from the start date of treatment to the onset date of event will be calculated, but the onset date of event will be the earlier date of hospitalization or death. Even if only either the status of hospitalization or the presence or absence of adverse events is reported, the date of hospitalization or death will be regarded as the onset date of event if hospitalization or death applicable to an event is confirmed. If the status of hospitalization is not reported and death is observed, it is acceptable to consider the date of death as the onset date of event because the status of hospitalization is unknown, although it may overestimate the time to event. If no event has occurred, the patient will be censored at the date of the last observation or Day 28 after the end of treatment, whichever is earlier. Even in

the case of unknown, the patient will be censored at the start date of treatment if neither the status of hospitalization nor the presence or absence of adverse events is reported and if the status of hospitalization is not reported and the patient has not died, or at the date of last observation or Day 28 after the end of treatment, whichever is earlier, if the presence or absence of adverse events is not reported and the patient has not been hospitalized.

- For the purposes of sensitivity analysis, hospitalization for the treatment of infection caused by SARS-CoV-2 is defined as follows. For hospitalizations not meeting this, the patient will be censored according to the above definition.
 - There are concomitant medications for infection caused by SARS-CoV-2 or concomitant non-drug therapies due to infection caused by SARS-CoV-2 on or after the date of admission.

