10. APPENDICES

10.1. Appendix 1: Handling of Efficacy-related Questionnaire Items in the Identification of Efficacy Analysis Sets

Table 1. Identification of Efficacy Analysis Sets 1 and 2

Case	Stat	Status of CRF entry		Safety Analysis Set‡	Efficacy	Efficacy Analysis Set 1†‡		Efficacy Analysis Set 2†‡			
	Adverse	Hospitali	Efficacy	Inclusion/	Inclusion/	Eval	uable	Inclusion/		Evaluable	
	event page	zation status page	evaluatio n page	exclusion (Reason)	exclusion (Reason)	Deaths	Severity related	exclusion (Reason)	Deaths	Hospitalization or death	Severity related
1	Yes	Yes	Yes	Included	Included	Yes	Yes	Included	Yes	Yes	Yes
2	No	Yes	Yes	Excluded (AE information)	Included	Unknown	Yes	Included	Unknown	Yes (only hospitalization events present) or unknown	Yes
3	Yes	No	Yes	Included	Included	Yes	Yes	Included	Yes	Yes (only death events present) or unknown	Yes
4	Yes	Yes	No	Included	Included	Yes	Unknown	Included	Yes	Yes	Unknown
5	No	No	Yes	Excluded (AE information)	Included	Unknown	Yes	Included	Unknown	Unknown	Yes
6	No	Yes	No	Excluded (AE information)	Included	Unknown	Unknown	Included	Unknown	Yes (only hospitalization events present) or unknown	Unknown
7	Yes	No	No	Included	Included	Yes	Unknown	Included	Yes	Yes (only death events present) or unknown	Unknown
8	No	No	No	Excluded (AE information)	Excluded (Efficacy information)	NA	NA	Excluded (Efficacy Set 1)	NA	NA	NA

AE, adverse event; NA, not evaluated due to exclusion from population

[‡] For the CRF pages to be used to identify the population other than the adverse event page, hospitalization status page, and efficacy evaluation page, it is assumed that there are no items meeting the exclusion criteria.

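### SAP 6.2 identifies death only from the adverse event outcome; a death recorded only as end-of-study status would be lost from the mortality and composite endpoints

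*SAP*

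**What the plan says.** SAP 6.2 defines all-cause death for Efficacy Analysis Sets 1, 2 and 3. Its only stated source is the adverse event record: "Death should be confirmed with the outcome information of adverse events". If that record is empty, the classification is "Unknown if no adverse event is reported (Section 10.1 Table 1"). The censoring rule begins: "If an event including the case of unknown has not occurred, the patient will be censored at the date of the last observation". It gives post-treatment Day 28 as a second limit, and the earlier of the two dates applies.

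The composite in Sets 2 and 3 uses the same source for death but has its own censoring. The earlier of last observation and Day 28 after the end of treatment applies "if the presence or absence of adverse events is not reported and the patient has not been hospitalized". A different rule covers patients for whom both items are missing: "the patient will be censored at the start date of treatment if neither the status of hospitalization nor the presence or absence of adverse events".

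Protocol 8.3.8 collects death a second time. For a patient not followed to Day 28 after treatment, the site must "record date of discontinuation and select only one of the following items that corresponds to the primary reason", and death is one of the items. The same section adds: "If the primary reason corresponds to patient death, necessary information should be recorded in the adverse event field".

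SAP 5.2 applies only conditions 1 to 5 of Section 5.1 to Efficacy Analysis Set 1. It drops condition 6, which covers patients seen again but with no adverse event information entered. In SAP 10.1 Table 1 these are cases 2, 5 and 6. The safety set marks them "Excluded (AE information"), while Efficacy Sets 1 and 2 include them with the Deaths column set to unknown.

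Protocol 8.7 plans a count of deaths for any reason and attaches no condition about the adverse event page.

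**The concern.** Two CRF fields can show that a patient died, and the endpoint derivation reads one of them. The efficacy sets admit patients for whom that one field may be empty. Table 1 then fixes the death result as unknown, with no exception for a patient whose end-of-study record says death.

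This matters because the study has one arm, so the absolute number of deaths is itself the result, and that number is likely to be small. The report could also disagree with itself. SAP 8.2.1.2 tabulates discontinuations by reason, and that table could show more deaths than the mortality analysis. There is an asymmetry as well: for a patient without an adverse event page, the composite accepts a hospitalisation recorded on another page but not a death recorded on another page.

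**Working it through.** The plan attaches no figure to the death rule, so there is nothing to reproduce. The check traces the rules and then illustrates size on assumed numbers.

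**Step 1: what happens to a patient with end-of-study status of death when queries do not resolve the gap.** Inputs: SAP 6.2, SAP 7 (a missing adverse event outcome is tabulated as unknown) and SAP 10.1 Table 1. In the table, 'earlier limit' means the earlier of last observation and Day 28 after the end of treatment.

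| Record | Death endpoint | Composite (Sets 2 and 3) |
|---|---|---|
| Adverse event page blank, hospitalisation page filled, no COVID-19 admission (cases 2, 6) | Unknown, censored at earlier limit | Unknown, censored at earlier limit |
| Same, with a COVID-19 admission | Unknown, censored at earlier limit | Event kept through the admission |
| Adverse event and hospitalisation pages blank, efficacy page filled (case 5) | Unknown, censored at earlier limit | Unknown, censored at treatment start |
| Adverse event page filled but outcome blank, hospitalisation page filled (cases 1, 4) | No fatal outcome found: non-event, censored at earlier limit | Event only if there was a COVID-19 admission; otherwise censored at earlier limit |
| Adverse event page filled but outcome blank, hospitalisation page blank (cases 3, 7) | Non-event, censored at earlier limit | Unknown, censored at treatment start |

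In every row the death itself is not counted. In the composite, the patient's event is lost only where there was no qualifying COVID-19 admission.

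**Step 2: direction.** Each affected patient removes one event and adds one censored observation, possibly censored on the day of death. Nothing in the rule adds a death, so the count can only fall.

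**Step 3: size, on assumed values.** The documents give neither a death rate nor a rate of blank adverse event pages. The relative loss from one missed death among D deaths is 1/D:
- D = 5: 1/5 = 20%
- D = 9: 1/9 = 11%
- D = 15: 1/15 = 7%

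For the absolute scale, take an assumed efficacy set of 3000. (The protocol's 3000 is the target for the safety set; it is borrowed here only as a round size.)
- 15 deaths, 3 of them unrecognised: 15/3000 = 0.50% (exact 95% CI 0.28% to 0.82%) becomes 12/3000 = 0.40% (0.21% to 0.70%). A Kaplan-Meier calculation with the 3 censored on their own death day falls from 0.500% to 0.400%.
- 6 deaths, with 5% to 30% unrecognised: 6 down to 4 counted, that is 0.20% down to 0.13%.
- 30 deaths, with 5% to 30% unrecognised: 28 down to 21 counted, that is 0.93% down to 0.70%, against a true 1.00%.
- If every site follows Protocol 8.3.8, the loss is zero.

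**The case against.** The strongest reply is that the adverse event page is the designed source for deaths. Protocol 8.3.8 sends a death to the adverse event field. Protocol 10.4 makes an event resulting in death a serious adverse event, and Protocol 10.1 requires every such event on the CRF and a report within 24 hours. Protocol 8.6.5.2 provides for queries. A site that follows these rules fills the page, and the patient is then no longer case 2, 5 or 6. Table 1 lists all eight combinations of three pages, so the presence of those cases says nothing about how often a patient who died falls into them. Patients with no re-visit and no adverse event information have already been removed by condition 5. The study is also non-confirmatory, and a list of deaths is planned in SAP 9.

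Most of this stands, and it limits the point to records where the entry or its outcome is missing and queries fail. It does not remove the point. The safeguard works through the same field that the endpoint depends on, and the SAP provides no fallback although a second field exists.

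Two stronger readings are not supported. A reader might infer that these patients are counted as survivors. They are not: they are labelled unknown, or counted as non-events where only the outcome is blank, and they leave the risk set at the censoring date. A reader might also infer that the end-of-study record supplies a date of death. Protocol 8.3.8 asks for a date of discontinuation or end of observation, so as a death date it is approximate.

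**Conclusion.** The point holds as a conditional weakness of the derivation rule, worth correcting because the remedy is cheap. Where the end-of-study status is death, the adverse event entry or its outcome is missing, and queries fail, SAP 6.2 loses a recorded death from the mortality endpoint. It also loses it from the composite unless there was a COVID-19 hospitalisation. The direction is certain: downward.

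The size is unknown and probably small, since the protocol directs deaths to the adverse event field. The percentages above rest on assumed death counts and assumed missing rates. They show that each death carries weight when there are few, not that any has been missed. It would be tempting to conclude that the study's mortality estimate is biased downward, but the documents do not show that such records exist.

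**What to change.** In SAP 6.2, for both death and the composite, define death as an adverse event outcome of fatal or an end-of-study status of death, within the evaluation window. Class death as unknown only if neither source is informative.

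Where no adverse event death date exists, apply the SAP 7 imputation for date of death. Add the end-of-study or discontinuation date to its list of candidate dates, and flag the resulting dates as approximate.

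Amend the Deaths and the Hospitalization-or-death columns of Table 1 to match. State that this rule, not the general SAP 7 rule setting inconsistent data to missing, governs a disagreement between the two fields. Reconcile the two fields before database release, and report how many deaths were found only through the end-of-study status.

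Both fields are already collected, so no new data are needed. The cost is an edit to two endpoint definitions, one date rule and Table 1, a small reconciliation step, and a few approximate death dates. The change does not reach patients excluded from Efficacy Set 1 altogether: Table 1 case 8 and those removed by condition 5.

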#### 8.3.4. Hospitalization status

Regarding the status of hospitalization during the observation period, the following information should be recorded.

- 1. Presence/absence of hospitalization during the observation period
- 2. Date of admission (reason for admission)/date of discharge

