5.2. Efficacy Analysis Set

Efficacy Analysis Set 1 will consist of the population excluding patients who meet any of the conditions 1, 2, 3, 4, and 5 in Section 5.1 and the conditions shown below.

- Efficacy cannot be evaluated appropriately because the condition for evaluating efficacy is not met
 (description in the report, "efficacy not evaluable")
 Condition: No adverse events are reported, the status of hospitalization is not reported, and both the
 presence or absence of worsening of severity after the start of treatment with this drug and the
 presence or absence of symptoms on the end date of the observation period are not reported.
- 2. Disease not subject to the study (description in the report, "disease not subject to the study") Condition: The disease name is other than infection caused by SARS-CoV-2.
- 3. Inadequate treatment period or dose (description in the report, "inadequate administration") Condition: Nirmatrelvir has not been administered.

Efficacy Analysis Set 2 will exclude patients who meet any of the following conditions from Efficacy Analysis Set 1.

4. The patient was not an outpatient at the start of treatment with this drug (description in the report, "other than outpatient at the start of treatment")

Condition: The patient was not an outpatient at the start of treatment with this drug.

Specific examples of identification methods for Efficacy Analysis Sets 1 and 2 are provided in Section 10.1 Table 1.

Efficacy Analysis Set 3 will exclude patients who meet the following conditions from Efficacy Analysis Set 2.

- 5. No risk factors for aggravation at the start of treatment with this drug (description in the report, "no risk factors for aggravation")
 - Condition: The patient does not meet any of the following risk factors for aggravation. If the age is unknown, it will be considered that the condition for risk factors for aggravation is not met. Similarly, when BMI cannot be calculated, smoking status is unknown or not provided, and medical history is unknown or not provided, it will be considered that each condition is not satisfied.
 - ≥60 years of age

- BMI $> 25 \text{ kg/m}^2$
- Smoking status "present" (a rough guide for "present": current smoking at the start of treatment with this drug [smoking within 30 days] and having smoked at least 100 cigarettes in their lifetime)

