8.1.4. Time (to event) data

Kaplan-Meier's method will be used to determine the median, 1st quartile, and 3rd quartile. The time point incidence will be calculated on Days 3, 5, 7, 14, 21, and 28 after the start of treatment with this drug (the start date of treatment will be defined as Day 1). Confidence intervals will be estimated using the log-log transformation (corresponding to specifying a loglog under the conftype option in the proc lifetest statement of the SAS®, lifetest procedure). In addition, Kaplan-Meier plots will be prepared.

When time data are compared between subgroups, the hazard ratio of events and its 95% confidence interval will be calculated using Cox proportional hazard model (Breslow method for handling ties). In addition, the hazard ratio and 95% confidence interval will be graphically presented.

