8.2.2. Patient characteristics and treatment history

8.2.2.1. Patient characteristics

In the safety analysis set, Efficacy Analysis Set 1, Efficacy Analysis Set 2, and Efficacy Analysis Set 3, the following patient characteristics will be summarized in accordance with Section 8.1:

- Sex [male, female]
- Age (continuous)
- Age [<15 years, \ge 15 years]
- Age [<65 years, ≥65 years]
- Age [<18 years, \ge 18 years]
- Age [<65 years, ≥65 to <75 years, ≥75 years]
- Age $[\ge 60 \text{ years}] * \ge 60 \text{ years}$ is a risk factor for aggravation.
- Age and body weight [\geq 12 to <18 years and \geq 40 kg, \geq 6 to <12 years and \geq 40 kg, \geq 6 to <18 years and \geq 20 to <40 kg, \geq 6 to <18 years and <20 kg, \geq 2 to <6 years, <2 years]

- Pregnancy [absent, present] * Female only
- Inpatient/outpatient status at the start of treatment with this drug [outpatient, inpatient]
- Reason for hospitalization at the start of treatment with this drug [treatment of infection caused by SARS-CoV-2, isolation, other]
- BMI [\leq 25 kg/m², >25 kg/m², unknown] * \geq 25 kg/m² is a risk factor for aggravation.
- Smoking status [no, smoked in the past, smoking, unknown] * "Smoking" is a risk factor for aggravation.
- Disease subject to the study [infection caused by SARS-CoV-2, other]
- Symptoms of infection caused by SARS-CoV-2 [present, absent, unknown]
- Number of days from the onset of symptoms of infection caused by SARS-CoV-2 to the start of treatment with this drug [within 3 days, 4 or 5 days, 6 days or more, unknown] (If the onset of symptoms and the start of treatment with this drug are observed on the same day, the number of days will be 0.)
- Severity of symptoms of infection caused by SARS-CoV-2 [mild, moderate I, moderate II, severe, unknown]
- Hepatic impairment [absent, present, unknown] [if present: mild, moderate, severe, unknown]
- Renal impairment [absent, present, unknown] [if present: mild, moderate, severe, unknown]
- Medical history [absent, present]
- History of infection caused by SARS-CoV-2 [absent, present]
- Complications [absent, present]
- Complications corresponding to risk factors for aggravation of infection caused by SARS-CoV-2
 [absent, present] * "Present" is a risk factor for aggravation.

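### In hospitalization-or-death (Efficacy Sets 2 and 3), patients with no hospitalization status stay in the risk set only if they die, so censoring depends on the outcome

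*SAP*

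**What the plan says.** SAP 6.2 defines the composite of hospitalization for SARS-CoV-2 infection or death from any cause for Efficacy Analysis Sets 2 and 3. Death is taken from adverse event outcomes and hospitalization from the hospitalization record (Protocol 8.3.4: "Presence/absence of hospitalization during the observation period").

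When hospitalization status is missing, SAP 6.2 has two rules:
- If the patient died, the death is an event on its own date. The SAP says that "it is acceptable to consider the date of death as the onset date of event because the status of hospitalization is unknown", and concedes only that time to event may be overstated.
- If the patient survived, "the patient will be censored at the start date of treatment". The condition for this is "if the status of hospitalization is not reported and the patient has not died". In SAP 8.1.4 "the start date of treatment will be defined as Day 1", so such a patient leaves on Day 1.

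Table 1 (SAP 10.1) shows the same for cases 3 and 7, which have an adverse event page and no hospitalization page. Both are included in Set 2, with the composite evaluable as "Yes (only death events present) or unknown".

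The reverse situation is handled differently. If adverse event information is missing and the patient was not hospitalized (within cases 2 and 6), follow-up continues without an event to the last observation or Day 28 after treatment, although survival is unknown.

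SAP 8.2.4.6 applies the time-to-event methods of SAP 8.1.4 and also reports the proportion of events. SAP 8.2.4.7 adds subgroup hazard ratios.

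**The concern.** Kaplan-Meier and Cox estimates require that leaving the risk set tells us nothing about the outcome. Here one missing-data group is split by its outcome: deaths keep their full time at risk, and survivors contribute none beyond Day 1. This does not depend on why the page is missing. Even pages lost purely by chance give a biased estimate, because the rule itself selects on the outcome.

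At stake are the incidence of the composite defined specifically for the outpatient sets and the subgroup hazard ratios. The hazard ratios are distorted where the levels of a factor differ in missing pages or in the share of events that are deaths. The SAP acknowledges a timing effect and does not mention the selection.

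**Working it through.** The documents give neither an expected rate for this endpoint nor a missing-page rate, so there is no figure of the plan's own to reproduce. The risks and missing-page shares below are assumptions.

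**Inputs**
- p: true risk of hospitalization or death, the same with and without the page (missing at random).
- d: risk of a reported death.
- m: share of the set with adverse event information but no hospitalization page (cases 3 and 7).
- No other censoring.

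**Step 1: formulas under the SAP rule**
- Events, as a share of the set: (1−m)p + m·d. Hospitalizations of no-page survivors are not seen.
- Patients at risk beyond Day 1: (1−m) + m·d.
- Kaplan-Meier incidence at the end of follow-up: [(1−m)p + m·d] / [(1−m) + m·d].
- Crude proportion over the whole set: (1−m)p + m·d. SAP 8.2.4.6 does not name the denominator, so the whole set is assumed.

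**Step 2: example with p = 2%, d = 0.6%, m = 10%**
- Events: 0.9 × 0.02 + 0.1 × 0.006 = 0.0186.
- At risk: 0.9 + 0.1 × 0.006 = 0.9006.
- Kaplan-Meier: 0.0186 / 0.9006 = 2.07%, against a true 2.00%.
- Crude proportion: 1.86%.

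A product-limit simulation with these inputs (400 runs of 3000 patients) gave 2.07% by Kaplan-Meier and 1.87% as the crude proportion. Leaving out all no-page patients gave 2.00%.

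**Step 3: other missing-page shares (p = 2%, d = 0.6%)**

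| m | Kaplan-Meier | Crude proportion |
|---|---|---|
| 2% | 2.012% | 1.972% |
| 5% | 2.031% | 1.930% |
| 10% | 2.065% | 1.860% |
| 20% | 2.147% | 1.720% |

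For p from 0.5% to 5%, d from 10% to 50% of p and m from 2% to 20%, Kaplan-Meier rises by about 0.2% to 12% in relative terms and the crude proportion falls by 1% to 18%. The rise belongs to later time points. Early on, no-page patients who will die later sit in the risk set without an event.

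**Step 4: subgroups**
Take two levels with the same true risk of 2%, one with no missing pages and one with m = 20%. The incidences are 2.00% and 2.147%, a ratio of 2.147 / 2.00 = 1.07 where the truth is 1. At risks this low, the hazard ratio would be close to this.

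**Step 5: the reverse rule**
Let q be the share with no adverse event information, followed as event-free unless hospitalized. Assume that every death occurs without a prior counted hospitalization. Incidence is then about p − q·d. With q = 10%: 2.00% − 0.1 × 0.6% = 1.94%.

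With both rules acting on separate groups (m = q = 10%):
- Events: 0.8 × 0.02 + 0.1 × 0.006 + 0.1 × (0.02 − 0.006) = 0.0180.
- At risk: 0.8 + 0.0006 + 0.1 = 0.9006.
- Kaplan-Meier: 0.0180 / 0.9006 = 2.00%.

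The two errors happen to cancel here; other values of m and q would not.

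**Step 6: pages not missing at random**
In the Step 2 example, let the no-page patients have true risk p0. The whole-set risk is 0.9 × 0.02 + 0.1 × p0. It equals the Kaplan-Meier value of 2.065% when p0 is about 2.65%, roughly 1.33 times the others' risk. Above that, Kaplan-Meier is too low.

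**The case against.** The strongest reply is that the study is single-arm and exploratory, names no primary endpoint, reports events and censoring separately and lists deaths. The rule also has a purpose: Protocol 8.7 tabulates patients hospitalized for the infection or dead from any cause, and dropping confirmed deaths would depart from that. This is a fair argument for keeping the deaths visible. It does not make outcome-dependent censoring valid for Kaplan-Meier or Cox.

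Four stronger readings are tempting, and the documents do not support them.
- **The incidence is always inflated.** Only late Kaplan-Meier incidence rises, and only if pages are missing at random. The crude proportion falls, and the reverse rule pulls down.
- **The inflation could reach 25%.** Suppose 1900 patients with the page have 38 events (2.00%) and 100 without it have 10 deaths. The estimate is 48/1910 = 2.51%, a quarter above 2.00%. But 2.00% is the risk only in patients with the page. The whole-set risk is at least 48/2000 = 2.40%, so the excess is at most about 5%. Three unseen hospitalizations make it 51/2000 = 2.55%, and the estimate is then too low. The 25% would hold only if those deaths were inpatients placed in Set 2 by mistake.
- **Undocumented patients default to outpatient.** SAP 5.2 excludes a patient if "The patient was not an outpatient at the start of treatment with this drug", and SAP 8.2.2.1 lists "Inpatient/outpatient status at the start of treatment with this drug [outpatient, inpatient" with no unknown level. But the dagger note on Table 1's efficacy columns is not in the text available here, nor is the CRF. The visible note says that other CRF pages also identify the sets, and SAP 7 gives missing categorical values a not-recorded category.
- **Case 5 patients count only if they die.** They have no adverse event page, so they can never be an event. They are always censored on Day 1, whatever the outcome.

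**Conclusion.** The point holds in a limited form. For patients with adverse event information but no hospitalization page (cases 3 and 7), SAP 6.2 makes censoring depend on the outcome. This biases the Kaplan-Meier incidence and can distort the subgroup hazard ratios. The handling is also not symmetrical with that for missing adverse event information, and one rule moves two planned outputs in opposite directions.

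The size cannot be fixed from the documents. With pages missing at random, 2% event risk, 0.6% death risk and 10% of pages missing, the bias is about 0.07 percentage points in late Kaplan-Meier incidence and about −0.14 in the crude proportion. If few pages are missing it is negligible. No net direction can be claimed. The finding itself, that the rule selects on the outcome, rests on the SAP text alone.

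**What to change.** In SAP 6.2 and 8.2.4.6, base the main hospitalization-or-death estimates (Kaplan-Meier, Cox and proportion) on Set 2 and Set 3 patients with both hospitalization status and adverse event information reported, which are Table 1 cases 1 and 4. State that population as the denominator of the proportion, and carry it into the hazard ratios of SAP 8.2.4.7.

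Keep the present SAP 6.2 rule as a sensitivity analysis. Report separately, for each of cases 2, 3, 5, 6 and 7, the number of patients and the deaths or hospitalizations observed. No confirmed death is then lost from the Protocol 8.7 tabulation, and readers can see how much is missing.

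The cost is one derivation rule, one extra analysis, a short table of counts and a slightly smaller main population. The complete-record estimate still assumes that pages are missing at random, and the SAP should say so.
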